11.3.6 Additional Follow-up at Day10

The following assessments will be performed:

- Blood samples for laboratory tests (according to schedule provided in Table 2)
 - Anti-drug antibodies (ADA)
 - Direct antibody test (direct Coombs)

12 STUDY METHODOLOGY

12.1 Medical History

All relevant medical history (diagnoses) available from patient records will be collected in the eCRF.

12.2 Previous and Concomitant Therapies

All treatments taken by the patients on entry to the study or at any time during the study in addition to the investigational product, are regarded as concomitant treatments and must be documented on the appropriate pages of the eCRF.

Concomitant medications will be recorded in the eCRF until 3 days after end of infusion (EOI).

Concomitant medications related to AEs (corrective drug required) should be recorded until D28.

Relevant previous treatments taken within 24 hours before the study must also be documented in the eCRF.

12.3 APACHE II Score

The Acute Physiology and Chronic Health Evaluation II score is a severity-of-disease classification system (21). It is generally applied within 24 hours of admission of a patient to an intensive care unit (ICU). An integer score from 0 to 71 is computed based on measurements of:

- $AaDO_2$ or PaO_2 (depending on FiO_2)
- Temperature (rectal)

- Mean arterial pressure
- pH arterial
- Heart rate
- Respiratory rate
- Sodium (serum)
- Potassium (serum)
- Creatinine
- Haematocrit
- White blood cell count
- Glasgow Coma Scale

Higher scores correspond to more severe disease and a higher risk of death.

Patients eligible for the study must not have an APACHE II Score of ≥ 34 or < 14 .

12.4 Vital Signs

Systolic and diastolic blood pressure and heart rate will be documented in the eCRF.

12.5 SOFA Score

The SOFA (sequential organ failure assessment) score is a scoring system to determine the extent of a person's organ function or rate of failure. It is based on six different scores, one each for the respiratory, cardiovascular, hepatic, coagulation, renal and neurological systems (22).

It will be calculated daily between screening and day 5 and at day 28 according to the following:

Respiratory System

PaO ₂ /FiO ₂ (mmHg)	SOFA Score
< 400	1
< 300	2
< 200 and mechanically ventilated	3
< 100 and mechanically ventilated	4

Nervous System

Glasgow coma scale	SOFA Score
13-14	1
10-12	2
6-9	3
< 6	4

Cardiovascular System

Mean arterial pressure OR administration of vasopressors required	SOFA Score
MAP < 70 mm/Hg	1
dop \leq 5 or dob (any dose)	2
dop > 5 OR epi \leq 0.1 OR nor \leq 0.1	3
dop > 15 OR epi > 0.1 OR nor > 0.1	4

Doses are in $\mu\text{g}/\text{kg}/\text{min}$; dop : dopamine ; dob : dobutamine ; epi : epinephrine ; nor : norepinephrine

Liver

Bilirubin (mg/dl) [μ mol/L]	SOFA Score
1.2–1.9 [> 20-32]	1
2.0–5.9 [33-101]	2
6.0–11.9 [102-204]	3
> 12.0 [> 204]	4

Coagulation

Platelets $\times 10^3$ /ml	SOFA Score
< 150	1
< 100	2
< 50	3
< 20	4

Kidneys

Creatinine (mg/dl) [μ mol/L] (or urine output)	SOFA Score
1.2–1.9 [110-170]	1
2.0–3.4 [171-299]	2
3.5–4.9 [300-440] (or < 500 ml/d)	3
> 5.0 [> 440] (or < 200 ml/d)	4

In cases where the physiological parameters do not match any row, zero points are given. In cases where the physiological parameters match more than one row, the row with most points is picked.

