9.2 Inclusion Criteria

To be eligible for the study, patients must meet the following criteria:

1. Provide written informed consent (proxy/legal representative/independent physician/emergency consent) according to local regulations
2. Age 18 to 80 years

Sepsis

3. Documented or suspected infection: lung, abdominal or elderly UTI (≥ 65 years)
4. Organ dysfunction defined as acute change in SOFA score ≥ 2 points

Shock

5. Refractory hypotension requiring vasopressors to maintain MAP ≥ 65 mm Hg despite adequate volume resuscitation of at least 20 ml/kg within 6 hours (according to Surviving Sepsis guidelines, see Appendix 1)
6. Hyperlactatemia (blood lactate > 2 mmol/l or 18 mg/dl). This criterion must be met at least once for the purpose of diagnosis within the 24 hours before study drug administration

9.3 Exclusion Criteria:

The presence of any of the following will exclude a patient from study enrolment:

1. Previous episode of septic shock (vasopressor administration) within current hospital stay
2. Underlying concurrent immunodepression (specified in appendix 2)
3. Solid organ transplant requiring immunosuppressive therapy
4. Known pregnancy (positive serum pregnancy test)
5. Prolonged QT syndrome (QTc ≥ 440 ms)
6. Shock of any other cause, e.g. hypotension related to gastrointestinal bleeding
7. Ongoing documented or suspected endocarditis, history of prosthetic heart valves
8. End-stage neurological disease
9. End-stage cirrhosis (Child Pugh Class C)
10. Acute Physiology And Chronic Health Evaluation (APACHE) II score ≥ 34
11. End stage chronic renal disease requiring chronic dialysis
12. Home oxygen therapy on a regular basis for > 6 h/day
13. Severe obesity (BMI ≥ 40)
14. Recent CPR (within current hospital stay)
15. Moribund patients
16. Decision to limit full care taken before obtaining informed consent
17. Participation in another interventional study in the 3 months prior to randomisation
18. APACHE II score < 14

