15.1.3 Endpoints

Safety and tolerability will be the primary endpoint and it will be monitored during the course of the study as specified below:

Safety and Tolerability Parameters

- Vital signs: systolic (SBP) and diastolic (DBP) blood pressure, heart rate, and body temperature.
- ECG (12-lead ECG)
- Safety laboratory tests: haematology, coagulation, plasma biochemistry.
- Presence of anti-LR12 antibodies
- Adverse events: from screening until study completion.

Secondary endpoints include the following:

Pharmacokinetics

Plasma concentrations of LR12 will be measured by a validated LC-MS/MS assay and analysed using non-compartmental methods to obtain estimates of the PK parameters.

Pharmacodynamics (exploratory)

The concentration profiles of biomarkers (sTREM-1, immune and vascular related biomarkers) over time and biomarker mRNA levels will be analysed.

Clinical Parameters

- Resolution of organ dysfunction (SOFA score total and individual domains)
- Vasopressor use
- Invasive mechanical ventilation
- Renal support
- Time until shock reversal defined as cessation of vasopressor support for 24 hours
- Mortality at day 28 and day 90

Safety and tolerability will be the primary endpoint and in addition, the exposure of MOTREM will be analysed. The biomarker concentration profiles over time and the area under the concentration (AUC) curves will be analysed as secondary PD variables.

The MOTREM concentration profile over time and the main derived PK parameters will be analysed as PK endpoints.

The endpoints and their analysis will be further specified in the statistical analysis plan (SAP).

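### The SOFA table in Section 12.5 leaves creatinine 5.0 and bilirubin 12.0 mg/dl unmatched, so its default rule scores them 0; the printed platelet unit also needs checking

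*Combined protocol and SAP*

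**What the plan says.** Section 12.5 gives one scoring table per organ system and two general rules. The default is: "In cases where the physiological parameters do not match any row, zero points are given". The tie rule is: "In cases where the physiological parameters match more than one row, the row with most points is picked".

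Each creatinine and bilirubin row carries an mg/dl limit with a µmol/L limit in brackets. For the kidneys, the 3-point row reads "3.5–4.9 [300-440] (or < 500 ml/d" and the 4-point row "> 5.0 [> 440] (or < 200 ml/d", each without its closing bracket here. For the liver, the 3-point row begins "6.0–11.9 [102-204" and the 4-point row is strictly above 12.0 mg/dl, or above 204 µmol/L. The section does not say which unit governs or how to round. The platelet column is headed "Platelets $\times 10^3$ /ml", with cut-offs of 150, 100, 50 and 20.

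The score is used in three places:
- Section 9.2, inclusion criterion 4: "Organ dysfunction defined as acute change in SOFA score ≥ 2 points".
- Section 15.1.3, as a clinical parameter: "Resolution of organ dysfunction (SOFA score total and individual domains". Section 15.1.5 has the total and each sub-score described by treatment group and visit.
- Sections 11.3.3 and 15.5, which add SOFA scores to day 5 for surviving patients, collected from source data for a post-hoc analysis with its own SAP.

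**The concern.** A loose table would normally be read sensibly at its edges. Here an explicit rule says what to do with a value that fits no row, and that rule assigns the best possible score. A result at the boundary of the top category would then be recorded as normal organ function, between a 3 on one side and a 4 on the other.

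The trial is multi-national and the table offers two units, so the same blood result could score differently according to the unit a laboratory reports.

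What is at stake is the descriptive account of organ dysfunction, in total and by domain, and above all the retrospective scores to day 5, for which a derivation rule has to be written down and applied to source values.

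**Working it through.** The plan states no figure to reproduce. The check applies the printed rows literally, with the default and tie rules of Section 12.5.

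**Inputs.** Row limits and rules are from Section 12.5, and 12 patients per dose level from Section 15.2. Conversion factors are not in the protocol and are assumed: 88 to 88.4 µmol/L per mg/dl for creatinine, 17.0 to 17.1 for bilirubin. The lower ends are the table's own ratios, 440/5.0 = 88 and 204/12.0 = 17.

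**1. One decimal, mg/dl limits.**

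| Analyte | Just below | Boundary | Just above |
|---|---|---|---|
| Creatinine | 4.9 → 3 | 5.0 → 0 | 5.1 → 4 |
| Bilirubin | 11.9 → 3 | 12.0 → 0 | 12.1 → 4 |

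From 1.2 to 8.0 mg/dl (69 values), 5.0 is the only creatinine value that scores 0. From 1.2 to 20.0 mg/dl (189 values), 12.0 is the only such bilirubin value.

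**2. Two decimals, mg/dl limits.**
- Creatinine: 1.91–1.99, 3.41–3.49 and 4.91–5.00 match no row, 9 + 9 + 10 = 28 values.
- Bilirubin: 1.91–1.99, 5.91–5.99 and 11.91–12.00 match no row, again 28.

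For each analyte, 10 of the 28 lie at the top boundary.

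**3. The same results by the µmol/L limits.**
- Creatinine 5.0 mg/dl: 5.0 × 88 = 440 → 3 points; 5.0 × 88.4 = 442 → 4 points.
- Bilirubin 12.0 mg/dl: 12.0 × 17.0 = 204 → 3 points; 12.0 × 17.1 = 205.2 → 4 points.

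In whole µmol/L the rows have no gaps. So the two unit columns disagree by 3 or 4 points for these two results.

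**4. Platelets.** One unit of 10^3 per ml is 1,000/1,000 = 1 platelet per µl, so the printed cut-offs equal 150, 100, 50 and 20 per µl. A count of 5,000 per µl is 5,000 × 10^3/ml, which is above every cut-off and scores 0. Read as 10^3/µl, the same count scores 4, and counts of 149, 99, 49 and 19 thousand per µl score 1, 2, 3 and 4.

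**5. Size in the endpoint.** A one-decimal creatinine course of 4.8, 5.0, 5.2 mg/dl would score 3, 0, 4: steady worsening shown with one day of apparent renal recovery. With 12 patients per group, one such error moves the group's mean total SOFA at that visit by 3/12 = 0.25 to 4/12 = 0.33.

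**6. Inclusion.** Criterion 5 requires vasopressors. In the cardiovascular table the lowest score for any listed agent is 2, and any epinephrine or norepinephrine dose scores 3 or 4. Exclusion criterion 1 bars an earlier vasopressor-treated septic shock in the same stay, so this change is ordinarily acute. Criterion 4 is then normally met without renal, liver or platelet points.

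**The case against.** The strongest reply is that a zero is not forced. Each row prints both units, so a creatinine of 5.0 mg/dl, once converted, does match a row and earns 3 or 4 points. That is a fair reading, but Section 12.5 neither asks for conversion nor says which limit prevails, and a site reporting in mg/dl would naturally use the mg/dl figures. The reply shows that the table contradicts itself between units; it does not remove the fault.

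Other points stand and limit the matter. Safety is the primary endpoint, the synopsis labels the clinical parameters exploratory, and SOFA is only described. Urine output below 500 or 200 ml/d still earns 3 or 4 renal points whatever the creatinine. The eCRF scoring and the data handling manual of Section 17.2 are not available, so the scores actually recorded may be right.

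A reader might infer three stronger things that the protocol does not support:
- **That severe renal or hepatic failure in general scores 0.** It does not: everything above 5.0 or 12.0 mg/dl scores 4. The count of 28 values is a count of grid points, not a frequency among patients.
- **That the coagulation domain is 0 for every trial patient.** This would require someone to have applied the printed unit literally, which nothing shows. The micro sign survives elsewhere in the same section, so a typing slip is as plausible as a reading error, but either would be a unit misprint.
- **That eligibility was compromised.** Required vasopressor use normally supplies the 2 points, and Section 9.4 adds central review before inclusion.

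**Conclusion.** The point holds as an error in a stated rule, with limited impact. By the mg/dl limits alone, one reportable value per organ at one decimal (28 per analyte at two decimals) falls through to 0. For creatinine 5.0 and bilirubin 12.0 the µmol/L limits give 3 or 4. The exact µmol/L score depends on the assumed conversion factor, but over the stated range it is never 0 for these two results.

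The platelet unit, as printed, is unusable with the printed cut-offs; whether the source document carries the same unit has to be checked.

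The consequence falls on the descriptive SOFA total and domain scores and on the retrospective derivation to day 5. It has little bearing on inclusion, and none is claimed for the primary safety endpoint or the sample size. Actual mis-scoring is not established.

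**What to change.** In Section 12.5:
- Make the mg/dl rows contiguous and consistent with the µmol/L column, so that every value falls in exactly one row, or state a rounding rule. The sponsor should settle whether 5.0 and 12.0 mg/dl belong to the 3- or 4-point row, and both columns should then agree.
- Limit the zero-point default to values better than the 1-point cut-off.
- Check the platelet unit against the source and, if the misprint is confirmed, correct it to × 10^3/µl.

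Carry the same rules into the SOFA derivation of the separate SAP announced in Section 15.5, and check any recorded creatinine, bilirubin and platelet scores at the affected boundaries against the raw values.

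The cost is a table correction and a short check in the derivation program. No design, sample size or eligibility change follows.

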12.6 Electrocardiographic (ECG) Measurements

12-lead ECGs will be recorded daily at the time-points described in the study plan in Table 1 on page 23. Copies of the ECG printouts will be collected by the sponsor.

12.7 Physical Examination, Height and Weight

Physical examinations will be performed as detailed in the Study Plan (Table 1).

A full physical examination includes an assessment of the following: eyes, ears, nose, throat, cardiovascular, respiratory, musculoskeletal, venous system, gastro-intestinal, lymphatic, dermatological and neurological system.

A brief physical examination will be symptom oriented and will not include specific parameters of full physical examination.

Height will be measured in centimetres and weight in kilograms. Where possible, measurements should be taken with patients wearing light clothing and without shoes using calibrated scales for all measurements. BMI will be calculated from the height and weight.

12.8 Requirement of Vasopressor, Mechanical Ventilation and Intubation

The beginning and end of study of vasopressor therapy, invasive mechanical ventilation and intubation will be documented in the eCRF.

12.9 Sepsis Related Clinical Events

Clinical events related to severe sepsis or sepsis complications will be collected. The following events will be considered clinical events related to severe sepsis or sepsis complications:

- Death related to severe sepsis, that is, related to severe sepsis or a sequela of sepsis based on the interpretation of the investigator.
- Cardiovascular events: the need for vasoactive drugs, hypotension.
- Respiratory events: decreased $\text{PaO}_2/\text{FiO}_2$, mechanical ventilation, hypoxia, acute respiratory distress syndrome, acute lung injury, or respiratory failure.
- Hepatic events: hepatic injury or liver dysfunction that leads to an increase from baseline in the serum level of bilirubin or other LFTs.
- Renal events: renal failure, renal insufficiency, or renal injury that leads to an increase from baseline in serum creatinine.
- Hematologic/coagulation events: coagulopathy, disseminated intravascular coagulation, thrombocytopenia, or thrombocytosis.
- Systemic inflammatory response syndrome related criteria: tachypnea, hypopnea, leukocytosis, leukopenia, hypothermia, tachycardia, or bradycardia.

12.10 Mortality Assessment

If a patient dies during the course of the study (time of informed consent to day 90 follow-up), the date and time of death will be documented. If possible, the cause of death will be documented.

12.11 Study Drug Infusion

The beginning and end of study of each drug infusion will be documented in the eCRF.

12.12 Duration of ICU Stay

The date and time of ICU discharge will be collected. This data will be collected to the extent available in source data and analysed post-hoc (see section 15.5).

12.13 Laboratory Tests

12.13.1 Local Laboratory Tests

The following laboratory tests will be performed at the clinical sites and the results will be transcribed into the clinical database

Haematology, Chemistry and Coagulation

Assessments of haematology, chemistry and coagulation will be performed according to Table 2 on page 25.

Pregnancy Test (Female Patients)

A serum beta-HCG pregnancy test will be performed on all women of childbearing potential prior to inclusion into the study.

Direct Antibody Test (Direct Coombs) – Sites in France only

A direct antibody test (direct Coombs test) will be performed at the time points specified in Table 2 on page 25.

Arterial Blood Gases

Partial pressure of arterial oxygen (PaO_2) and carbon dioxide (PaCO_2) and pH will be documented at the time points specified in Table 2 on page 25.

12.13.2 Centralised Laboratory Tests

All centralised laboratory tests and procedures are described in detail in a separate manual.

Biomarkers and RNA Profiles

Blood samples for the assessment of biomarkers and RNA profiles will be collected throughout the study according to Table 2 on page 25. Details for sampling requirements, storage and shipment to the respective laboratories are described in the SOM.

Pharmacokinetic Assessments

For timing of individual samples refer to the Study Plan (Table 1 and Table 2). The date and time of collection will be recorded on the appropriate eCRF.

PK Blood Samples: Venous blood samples for the determination of concentrations of LR12 (active ingredient of MOTREM) in plasma will be taken at the times presented in the Study Schedule (Table 1 and Table 2).

All sample handling procedures, including the time of each sample collection, the time of placement into frozen storage (at the end of the sample workup), will be documented in detail in the laboratory manual. The procedures and materials used, e.g. collection and storage tubes, were examined prior to any analytical measurements as part of the analytical method validation, to rule out any possible interference with the analyte.

Immunogenicity

The presence of anti-drug antibodies (ADA) will be assessed as described in Table 1 and Table 2. A venous blood sample will be collected for evaluation of anti-drug antibody presence for all patients at the selected time-points. Further details and sample analysis will be described in the laboratory manual.

12.13.3 Plasma Sample for Retention

A plasma sample for future exploratory analyses of biomarkers as described in Table 1 and Table 2 will be retained for all patients. The specimen will be used to achieve the following objectives:

- To study the association of biomarkers with efficacy of MOTREM treatment, adverse events or disease progression
- To increase knowledge and understanding of the septic shock disease biology

All biomarker samples will be destroyed no later than 5 years after the Clinical study report has been completed. However, the storage period will be in accordance to the ICF approved by the ethics committee and applicable laws.

All biomarker specimen will be subject to the confidentiality standards described in section 17.5.

12.13.4 Blood Sample for Pharmacogenetic Analysis

Certain polymorphisms in the gene coding for the TREM-1 and related genes could have an effect on the safety and efficacy of MOTREM. Therefore, one small blood sample for the future

exploratory analysis of these polymorphisms will be collected as described in Table 1 and Table 2. The total volume of blood sampling will remain unchanged as specified in section 12.12.5 below.

All biomarker samples will be destroyed no later than 5 years after the Clinical study report has been completed. However, the storage period will be in accordance to the ICF approved by the ethics committee and applicable laws.

All specimens will be subject to the confidentiality standards described in section 17.5.

The participation in this part of the study is voluntary and covered by a separate ICF.

12.13.5 Volume of Blood Sampling

Total blood volume sampled during the study in addition to standard care for each patient will be approximately 160 mL.

The total volume of blood that will be drawn from each patient in this study will be further specified in study operations manual. The actual amount withdrawn may be different per patient in case samples need to be repeated for technical reasons but will not exceed 250 mL.

12.13.6 Analysis and Storage of Blood Samples

All blood samples will be collected, processed, and reported as necessary for the purpose of the trial according to the study protocol.

Some of the blood samples will be analysed in the hospital's laboratory and are part of the patient's routine care. When the results are available, the samples will be destroyed according to the hospital's regulations.

Some of the blood samples will be sent to external laboratories for analysis. To maintain confidentiality, these samples will be coded and will not contain any personal identifying information.

Two serum samples will be stored for the purpose of studying specific characteristics predicting whether individual patients have a better or worse chance to respond to the treatment. Since these markers are still under investigation, we may need to do further research with these samples once the trial is finished. The samples will be kept in a secure place for up to 5 years and will be destroyed when the investigated results become available. Unused blood samples from external laboratories described above, may be used for exploratory analyses and will be treated accordingly.

One blood sample for exploratory pharmacogenetic analyses will be kept in a secure place, for up to 5 years and will be destroyed when the investigated results become available. The blood samples for DNA analysis will be double coded (two independent coding steps).

13 ADVERSE EVENTS

13.1 Adverse Events

Safety will be determined by an evaluation of physical examination, vital signs, ECG parameters, laboratory tests and by the occurrence of Adverse Events (AEs).

Adverse event (AE): Any untoward medical occurrence in a patient or clinical study subject administered a medicinal product and which does not necessarily have a causal relationship with this treatment. Events occurring prior to the first administration are part of baseline information.

An adverse event (AE) can therefore be any unfavourable and unintended sign (including an abnormal laboratory finding), symptom, or disease temporally associated with the use of an investigational medicinal product, whether or not considered related to the investigational medicinal product.

Adverse reaction (AR): All untoward and unintended responses to an IMP related to any dose administered.

All adverse events judged by either the reporting investigator or sponsor as having a reasonable suspected causal relationship to an investigational medicinal product are qualified as adverse reactions. The expression reasonable causal relationship means that there is evidence or argument to suggest a causal relationship.

Multiple signs or symptoms: If an AE consists of several signs or symptoms that can be represented by one single syndrome or diagnosis, the syndrome or diagnosis will be recorded in the CRF as the AE instead of the individual signs or symptoms.

Worsening: Signs, symptoms, syndromes or diagnoses present before the first administration of the IMP will be considered as AEs if they worsen after the start of the IMP.

AE collection: The condition of the patients will be monitored throughout the study from the time of signed Informed Consent up to the end of the study (day 28). The investigator will collect the AEs reported spontaneously, observed, or elicited in response to a non-leading question (for example, "How have you been feeling since we last asked you?"). The investigator will record all AEs in the source records and the eCRF.

Study specific definition:

Clinical events related to severe sepsis or sepsis complications are recorded on the appropriate eCRFs (see section 12.9). When serious, these clinical events are exempt from serious adverse event reporting, unless the investigator deems the event to be related to the administration of the study drug. The following events will be considered clinical events related to severe sepsis or sepsis complications:

- Death related to severe sepsis, that is, related to severe sepsis or a sequela of sepsis based on the interpretation of the investigator.
- Cardiovascular events: the need for vasoactive drugs, hypotension.
- Respiratory events: decreased $\text{PaO}_2/\text{FiO}_2$, mechanical ventilation, hypoxia, acute respiratory distress syndrome, acute lung injury, or respiratory failure.
- Hepatic events: hepatic injury or liver dysfunction that leads to an increase from baseline in the serum level of bilirubin or other LFTs.
- Renal events: renal failure, renal insufficiency, or renal injury that leads to an increase from baseline in serum creatinine.
- Hematologic/coagulation events: coagulopathy, disseminated intravascular coagulation, thrombocytopenia, or thrombocytosis.
- Systemic inflammatory response syndrome related criteria: tachypnea, hypopnea, leukocytosis, leukopenia, hypothermia, hyperthermia, tachycardia, or bradycardia.

AE rating:

The assessment of intensity of an AE will be made using the following general categorical descriptors:

Mild	No interference with the patient's daily activities and does not require mandatory corrective/symptomatic treatment
-------------	---

Moderate Moderate interference with the patient's daily activities and/or requires minimal medical intervention or corrective treatment required

Severe Major and unacceptable interference with the patient's daily activities and requires mandatory corrective/symptomatic treatment, possible hospitalisation

The investigator should use clinical judgment in assessing the intensity of events not directly experienced by the patient (e.g., laboratory abnormalities).

The causal relationship of AEs will be rated as either **related** or **unrelated** to the IMP.

The causal relationship of a SAE to the IMP will be rated as follows:

Unrelated Clearly and incontrovertibly due only to extraneous causes, and does not meet criteria listed under unlikely, possible or probable.

Unlikely Does not follow a reasonable temporal sequence from administration of the IMP, or is most likely related to another etiology than the trial drug such as the patient's clinical state, environmental factors or other therapies.

Possible Follows a reasonable temporal sequence from administration of the IMP, and/or a causal relationship cannot be excluded and remains likely.

Probable Good reason (such as clear-cut temporal association with improvement on cessation of the IMP or reduction in dose, or reappears upon (accidental) rechallenge, or follows a known pattern of response to the IMP) and sufficient documentation to assume a causal relationship.

The action taken with the IMP for an AE will be rated as: product withdrawn, dosing interrupted, dose not changed, not applicable. AEs requiring therapy will be treated with recognised standards of medical care to protect the health and the well-being of the patient.

The outcome of an AE will be rated as recovered, recovering, not recovered, recovered with sequelae, fatal or unknown. The investigator will follow up any AE until it is resolved or until the medical condition of the patient is stable. All relevant follow-up information will be collected. For AEs that are ongoing at the last visit, the investigator will make thorough efforts to document the outcome.

